### **7.5.2. Drug Accountability**

The study pharmacist and Investigator must maintain accurate records of dates and quantities of product(s) received, to whom dispensed (subject-by-subject accounting), and accounts of any product accidentally or deliberately destroyed. The Investigator must retain all unused and/or expired study supplies until the study monitor has confirmed the accountability data.

## **7.6. Treatment Compliance**

Subjects will be screened within a period not to exceed 28 days prior to Day 1.

The initial treatment period, including dose escalation, will be up to 12 weeks. Subjects who are not Treatment Failures and who otherwise meet criteria for continuation may continue treatment for up to an additional 40 weeks to assess achievement of remission and duration of response. All subjects should be followed for 4 weeks (28 days) after the last CCX140-B dose administered.

The CCX140-B tablets will be self-administered by participating study subjects. The morning dose of study drug on Day 1 will be taken in the presence of study site personnel. Subjects will be provided with dosing instructions at the start of the study, and will be encouraged by study site personnel to take the study medication according to the instructions for the duration of the

study. Subjects will be instructed to bring the assigned bottles of study medication to the site staff at each study visit, whether empty or not. The Investigator or designee should review each subject's dosing diary at each relevant visit, reconcile them against the study medication that each subject returns, document reasons for any discrepancies and calculate the dosing compliance rate. This information will be recorded and entered into the electronic data capture (EDC) system. Subjects that do not take at least 85% of the study medication can be discontinued from the study for non-compliance.

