### **8.2. Efficacy Analysis**

#### **8.2.1. Primary Endpoint Analysis**

The Primary Efficacy Objective is to evaluate the effect of CCX140-B on proteinuria in subjects with primary FSGS with nephrotic syndrome, assessed as a median reduction from baseline of urine protein to creatinine ratio (UPCR) of at least 20%, i.e.  $\geq 20\%$ , by week 12.

The assumed treatment effect for this study is based on efficacy findings with 5 and 10 mg CCX140-B once daily in study CL005\_140 in patients with diabetic nephropathy and proteinuria. In a pre-specified subset analysis, the greatest percentage improvement of UACR at approximately 12 weeks from baseline was observed in subjects who presented with the highest baseline UACR (801-3000 mg/g) and eGFR of at least 60 mL/min/1.73m^2. This subgroup receiving 5 (N=10) or 10 mg (N=13) of CCX140-B once daily showed a median reduction in

UACR of approximately 20%-30% receiving CCX140-B while patients receiving placebo (N=12) showed an increase of approximately 12%.

Based on these data, it is assumed that the median reduction from baseline UPCR is at least 20% by week 12 in the planned study CL012\_140. If the final observed data are consistent with this assumption, i.e. the previous positive study results are replicated in the FSGS population, the study will be considered positive in assessing the efficacy of CCX140-B.

Otherwise, if the observed data are consistent with the median reduction of below 20%, the study would not be considered positive.

After all of the initial 6 subjects have completed their 12-week of treatment the study will be paused and assessed. If the overall study results are deemed safe and the subjects' responses to treatment are considered clinically meaningful seven additional subjects will be treated for a total of 13 subjects.

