## **8.4. Sample Size Assumptions**

Six (6) male or female adult subjects with biopsy-proven primary FSGS and nephrotic syndrome will be enrolled into the first stage of this study, which is followed by another seven subjects after the data review of the initial 6 patients. The relatively small sample size is selected based on the exploratory safety and efficacy nature of the study. After all of the initial 6 subjects have completed their 12-week of treatment the study will be paused and assessed safety and efficacy. If the overall study results are deemed safe and the subjects' responses to treatment are considered clinically meaningful seven additional subjects will be treated for a total of 13 subjects.

Further details will be specified in the SAP.

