## **8.8. Treatment Compliance**

Exposure will be summarized by dose at each visit as well as total dose and average weekly dose.

CCX140-B plasma concentration measurements over the course of the study may also be used to assess subject compliance. Any events of non-compliance to the protocol will be documented in the study records. Non-compliant study subjects whose dosing compliance rate is less than 85% may be withdrawn from study.

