### 3.1.5 *Hypothesis Testing*

Since this is a small open-label study with one treatment group, formal hypothesis testing is not applicable.

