## 6 CHANGES FROM PROTOCOL-SPECIFIED STATISTICAL ANALYSES

There are several changes to the protocol-specified statistical analyses provided below:

- Due to the small sample size and abbreviated summary of data, no per-protocol analyses will be carried out.
- Primary endpoint analysis changed from assessing median reduction from Baseline to Week 12 of UPCR of at least 20%, to producing summary statistics for UPCR and eGFR.
- Secondary endpoint analyses have been removed. Instead this data will be listed, including:
  - Time-to-Event analysis for Partial Remission and/or Complete Remission
  - Proportion of subjects with Partial Remission or Complete Remission
  - Change from Baseline Serum Albumin over time
  - Change in UACR from Baseline over time
  - Time to investigator or physician initiation of rescue therapy including glucocorticoids, new immunosuppressive agents, or new major treatment modalities
  - Duration between achievement of remission and relapse or treatment failure
  - Changes over time in Health Quality Assessment (SF-36 v2 and EQ-5D-5L)

Rationale: Following study CL011\_140, a randomized, double-blind, placebo-controlled dose-ranging study to evaluate the safety and efficacy of CCX140-B in subjects with Focal Segmental Glomerulosclerosis (FSGS), its results did not support the development of CCX140 in FSGS. Therefore a decision was made to not continue enrollment in study CL012\_140, which also investigates CCX140 in patients with FSGS and nephrotic syndrome. In addition, the efficacy and safety summaries will be limited to specific parameters and an abbreviated CSR will be developed for this study.

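### Discretionary withdrawal from the study for compliance below 85% can leave the Week 12 UPCR missing, with no rule for handling it, in a trial of 6 to 13 subjects

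*Protocol*

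**What the plan says.** Protocol section 7.6 has the investigator or a designee reconcile diary and returned tablets at each relevant visit and calculate a compliance rate. It then adds: "Subjects that do not take at least 85% of the study medication can be discontinued from the study for non-compliance". Section 8.8 says the same: "Non-compliant study subjects whose dosing compliance rate is less than 85% may be withdrawn from study". Neither section says who decides, over what period the 85% is judged, or whether a Week 12 urine is still to be collected.

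The trial has one open-label arm. Six subjects are treated first, and if the review is favourable "seven additional subjects will be treated for a total of 13 subjects". The number rests on no power calculation: "The relatively small sample size is selected based on the exploratory safety and efficacy nature of the study".

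Protocol section 8.2.1 ties success to a median UPCR reduction of at least 20% by Week 12; if the data agree, "the study will be considered positive in assessing the efficacy of CCX140-B". SAP section 6 changes the primary analysis from that criterion "to producing summary statistics for UPCR and eGFR", and SAP section 3.1.5 states: "Since this is a small open-label study with one treatment group, formal hypothesis testing is not applicable". SAP section 3.4.1 keeps change and percent change in UPCR to Week 12 as the primary summary.

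The 85% condition on analysis belonged to the per-protocol set (protocol section 8.5.2). The SAP drops that analysis: "no per-protocol analyses will be carried out".

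**The concern.** Withdrawal from the study ends data collection as well as dosing. Compliance is judged while response is known: the Day 15, 43 and 71 escalation rules in protocol Table 1 depend on whether the subject has reached partial remission, so sites need UPCR results over the same weeks. Subjects may also skip doses because the drug is not helping or is poorly tolerated. The documents give no data on that link, so it is a possibility, not a fact.

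If subjects leave in this way before Week 12, the Week 12 median is taken over those who remain. With 6 to 13 subjects, one or two values can move it noticeably. Non-compliance is not itself a Treatment Failure criterion, and the SAP plans no sensitivity analysis that would show the effect.

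**Working it through.** **Is there a stated figure to reproduce?** The current text gives no power, alpha or SD behind the sample size; 13 is 6 + 7.

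**When does a withdrawal leave Week 12 empty?**
- Protocol section 7.4 requires Early Termination procedures for early withdrawals, and section 6.18 includes a 24-hour urine among them.
- SAP section 3.1.2 places that result by its actual date, using midpoints between scheduled assessments of the parameter.
- 24-hour urine is scheduled at Days 57 and 85: (57 + 85)/2 = 71, so the Week 12 window opens at Day 72. The SAP's eGFR example also gives Days 72 to 99.
- Spot UPCR is also collected at Day 71: (71 + 85)/2 = 78, so its window opens at about Day 78–79.
- Drug accountability before Week 12 falls nominally at Days 15, 29, 43, 57 and 71. Prompt withdrawal at any of the first four puts the termination urine before Day 72. Day 71 is borderline, given the ±3-day visit window and the time needed for a collection.
- SAP section 3.1.4 summarises non-missing values. Appendix A imputes dates only, so no rule covers a missing UPCR.

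**How much could one loss matter?** Assume that log UPCR ratios (Week 12 to baseline) are normal with mean 0 (no drug effect) and SD σ. The documents give no σ, so I use 0.3 to 0.8. The chance that a single subject shows a reduction of at least 20% is p = Φ(ln 0.8/σ), with ln 0.8 = −0.223:
- σ = 0.3: p = 0.2285
- σ = 0.5: p = 0.3277
- σ = 0.8: p = 0.3901

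For an odd number of values, the chance that the median shows at least a 20% reduction is an exact binomial tail. With 6 subjects and the worst one missing, the median of the remaining 5 is the 3rd best, giving P(X ≥ 3 of 6). With all 13 present it is P(X ≥ 7 of 13). For an even number of values I used simulation, taking the median on the log scale.

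| Case (null drug) | σ = 0.3 | σ = 0.5 | σ = 0.8 |
|---|---|---|---|
| 6 subjects, none lost (simulated) | 5% | 17% | 27% |
| 6 subjects, worst lost (exact) | 13.7% | 30.9% | 43.5% |
| 13 subjects, none lost (exact) | 1.5% | 9.6% | 20.7% |
| 13 subjects, worst lost (simulated) | 2.5% | 14% | 29% |

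Taking medians of percent changes instead lowers the even-numbered cases slightly: 5.1%, 15.8% and 25.6% in the first row; 2.5%, 14.1% and 28.1% in the last.

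**Shift in the reported median.** This matters more than a threshold under a descriptive SAP. At σ = 0.5, losing the worst subject moves the median log ratio on average by −0.101 (6 subjects) or −0.048 (13 subjects). That is exp(−0.101) − 1 = −9.6% and exp(−0.048) − 1 = −4.7%. The shift is proportional to σ. Over 0.3 to 0.8 it is −0.061 to −0.162 with 6 subjects (−6% to −15%) and −0.029 to −0.077 with 13 (−3% to −7%).

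**If the loss is unrelated to response.** At σ = 0.5 the chance goes from 17% to P(X ≥ 3 of 5) = 20% with 6 subjects, and stays at about 9.6% with 13. The median does not shift on average. The small rise with 6 comes from having 5 values instead of 6, not from bias.

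**The case against.** A reader might infer that poor responders can be removed at will. The documents do not support that: the trigger is compliance below 85%, found from diaries and returned tablets with reasons for discrepancies documented. A compliant poor responder cannot be withdrawn under this rule.

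A reader might also infer that the rule rebuilds the per-protocol exclusion inside the ITT result. It does not. ITT in SAP section 3.2.1 needs only a dose and one post-baseline efficacy assessment. A withdrawn subject stays in that set and in the earlier by-visit summaries, and an Early Termination value from about Day 72 counts as Week 12 for the 24-hour UPCR.

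Nor would such losses be hidden. Withdrawals are presented with reasons (SAP section 3.3.1), compliance is listed (3.3.8) and the number of non-missing values is reported (3.1.4). A claim that safety follow-up is cut off is also too strong: section 7.6 says all subjects should be followed for 28 days after the last dose, and section 7.3.7 continues SAE reporting for 90 days.

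Finally, the probabilities above depend on assuming that the lost subject is the worst responder, on an assumed SD, and on a 20% threshold that no longer decides anything. SAP section 1 adds that enrolment was not continued.

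All of this stands, and it limits the point to missing data. It does not remove the gap before about Day 72: being in the ITT population does not supply a Week 12 value, and listing a withdrawal does not correct a median computed without it.

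**Conclusion.** The concern holds as a missing-data point. A stated rule permits avoidable loss of the primary Week 12 UPCR, possibly related to response, and the SAP has no way of handling the loss. In the worst case, one lost subject improves the apparent median UPCR ratio by about 6–15% with 6 subjects or 3–7% with 13, and raises the chance of a null drug showing a 20% median reduction as tabulated. These figures assume no drug effect, normal log ratios with SD 0.3 to 0.8, one loss, and that the loss is the worst responder. If the loss is unrelated to response, the effect is negligible. How many subjects, if any, would be withdrawn under the rule is unknown.

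Because the SAP is descriptive, the consequence is a distorted primary summary and not a wrong formal decision. This is a cheap improvement, not a fatal flaw.

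**What to change.** These changes concern data collection and analysis only.

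- **Protocol sections 7.6 and 8.8:** replace withdrawal from the study with the following. Compliance below 85% is recorded as non-compliance; the subject remains in the study and provides the Week 12 24-hour urine, laboratory tests and follow-up, whether or not dosing continues. A subject's own withdrawal of consent is unaffected.
- **SAP section 3.4.1:** list each ITT subject without a Week 12 UPCR, with the reason and the last available value.
- **SAP section 3.4.1:** add a sensitivity summary that counts these subjects as not reaching a 20% reduction. For example, 3 of 5 observed (60%) becomes 3 of 6 (50%), and 6 of 12 (50%) becomes 6 of 13 (46%). This is deliberately conservative if the loss had nothing to do with response.

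The cost is a few remaining visits for subjects already enrolled and one extra summary. If the protocol wording can no longer take effect, the two SAP items can still be added before database lock.

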## 7.7. Concomitant Medications and Restrictions

The doses of RAAS inhibitors must be stable prior to Day 1, and remain stable throughout the course of the study, unless adjustment is required for the safety of the subject. For eligible subjects willing to participate in the Open-Label Extension (after Week 12), the doses of RAAS inhibitors and other concomitant drugs may be modified per physician judgment. Subjects who require addition of a new immunosuppressive or immunomodulatory agent may continue treatment with CCX140-B if they have not met criteria for treatment failure, the case has been discussed with the study director and there is agreement to continue treatment. Plasmapheresis is not allowed at any point during the course of the study.

CCX140-B is primarily cleared through CYP3A4 metabolism. Subjects taking strong CYP3A4 inducers (e.g., phenytoin, rifampicin, carbamazepine, St. John's Wort) will be excluded from this clinical trial since these drugs may substantially reduce the CCX140-B plasma levels. In addition, subjects taking strong CYP3A4 inhibitors (e.g., boceprevir, clarithromycin, conivaptan, grapefruit juice, indinavir, itraconazole, ketoconazole, lopinavir/ritonavir, mibefradil, nefazodone, nelfinavir, posaconazole, ritonavir, saquinavir, telaprevir, telithromycin, and voriconazole) will be excluded as these drugs may substantially increase the CCX140-B plasma levels.

All concomitant medications taken during the course and up to 12 weeks prior to screening Day 1 study should be recorded meticulously on the concomitant medication pages of the CRF.

Prior treatment with rituximab or other anti-CD20 monoclonal antibodies and corresponding levels of CD20+ B cells need to be recorded up to 1 year prior to screening.

Eligible patients who have entered the study on a continuous cycle therapy of rituximab or other anti-CD20 monoclonal antibodies need to remain on an unchanged therapy throughout the study at a dosing interval that has been documented to achieve continuous B cell depletion for the given patient unless prohibited due to safety considerations. Their levels of CD20+ B cells that are routinely evaluated per standard of care with anti-CD20 monoclonal antibody therapy need to be recorded throughout the study. Record UPCR and urine protein assessments up to 1 year prior to screening (if available) in the medical history if patients were treated with Rituximab, other CD20+ monoclonal antibodies, calcineurin inhibitors or other immunotherapy.

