## Methodology

This is an open label clinical trial to test the efficacy, safety, pharmacokinetics and tolerability of ascending doses of CCX140-B in subjects with primary FSGS and nephrotic syndrome. Throughout the treatment period, any changes in background medications should be limited to settings in which the Investigator deems it to be necessary for the safety of the subject.

Eligibility requirements are detailed in the inclusion and exclusion criteria.

The screening period will be up to 28 days.

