#### **4.2. Inclusion Criteria**

1. Male or female subjects aged 18 years and older
2. Renal biopsy findings consistent with diagnosis of focal segmental glomerulosclerosis (FSGS), and consistent with primary FSGS based on presentation of histopathology, medical history, and clinical course; subjects with genetic risk factors with presentations that are otherwise consistent with primary FSGS may also be enrolled.
3. Urinary total protein:creatinine ratio (UPCR)  $\geq 3.5$  g protein/g creatinine at screening, based on sample drawn from a 24-hour collection
4. Hypoalbuminemia of less than 3.5 g/dL
5. Estimated glomerular filtration rate (eGFR)  $>30$  mL/min/1.73m^2, as calculated using the Chronic Kidney Disease Epidemiology Collaboration (CKD\_EPI) equation (using creatinine or cystatin C)
6. If used, RAAS inhibitor dose, including doses of angiotensin converting enzyme inhibitor and/or angiotensin II receptor antagonist must have been started at least 4 weeks prior to Study Day 1, and projected to remain stable throughout the course of the study unless adjustment is required for management of hypertension.
7. Female subjects of childbearing potential may participate if adequate contraception is used during, and for at least 5 half-lives after last dose of study drug. Male subjects with partners of childbearing potential may participate in the study if they had a vasectomy at least 6 months prior to randomization or if adequate contraception is used during, and for at least one month after the last dose of study drug. Adequate contraception is defined as resulting in a failure rate of less than 1% per year (combined estrogen and progestogen [oral, intravaginal, or transdermal], or progestogen-only hormonal contraception (oral, injectable, or implantable), intra-uterine device, intra-uterine hormone releasing system, bilateral tubal occlusion, vasectomized partner, or sexual abstinence). In addition, a barrier method (i.e. cervical cap, diaphragm or condom) must be used during intercourse between a male subject and a female of child-bearing potential.
8. Willing and able to give written Informed Consent and to comply with the requirements of the study protocol

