### 7.7.1. Rescue Therapy

If the investigator decides that a subject needs to receive rescue therapy the subject will be considered a treatment failure. Rescue therapy is considered any new therapy or required dose increase of an existing concomitant therapy (other than allowed per [Section 7.7. Concomitant](#)

Medications and Restrictions) that is required for the safety of the patient and to treat the underlying disease of FSGS.

This would include but is not limited to the initiation of high dose glucocorticoid therapy, new immunosuppressive agents such as calcineurin inhibitors, cyclophosphamide, MMF, monoclonal antibodies, or other major treatments (e.g. plasmapheresis, dialysis).

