### 3.4.1 *Primary Efficacy Endpoints*

#### Primary Analysis

The primary efficacy endpoint analysis will include the following parameters: UPCR (Morning void), UPCR (24 hour Urine), and eGFR. This will be summarized by treatment group over time using descriptive statistics. Both change from baseline to Week 12, and percent change from baseline to Week 12 will be included in the summary.

Change and percent change from baseline in renal function will be based on eGFR (calculated using the CKD-EPI Cystatin C equation, the CKD-EPI Creatinine equation, the CKD-EPI Other Efficacy Endpoints

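### Protocol Section 7.7 permits discretionary background-drug dose changes after Week 12 that other sections limit to safety need, and some of them may count as neither rescue nor treatment failure

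*Protocol*

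**What the plan says.** **Rules that limit change.** The synopsis (Methodology) and Section 3.1.3 carry the same sentence: "Throughout the treatment period, any changes in background medications should be limited to settings in which the Investigator deems it to be necessary", the need being the subject's safety. Inclusion criterion 6 (synopsis and Section 4.2) wants the RAAS inhibitor dose "projected to remain stable throughout the course of the study unless adjustment is required for management of hypertension". Section 7.7 itself first says that RAAS doses must "remain stable throughout the course of the study, unless adjustment is required for the safety of the subject". Subjects on continuous anti-CD20 treatment "need to remain on an unchanged therapy throughout the study", with a safety exception (Section 7.7).

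**Rule that permits change.** For subjects in the extension, Section 7.7 says "the doses of RAAS inhibitors and other concomitant drugs may be modified per physician judgment".

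**Rescue and failure.** Section 7.7.1 counts as rescue a new therapy or a "required dose increase of an existing concomitant therapy (other than allowed per" Section 7.7), when it is needed for safety and to treat FSGS. A subject who needs rescue is a treatment failure. Treatment Failure criterion 2 (synopsis, Section 5.2.1, SAP 2.2.3) names rescue glucocorticoids, new immunomodulatory or immunosuppressive therapy, plasmapheresis and dialysis.

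**Analysis.** SAP 3.4.1 says of UPCR and eGFR: "This will be summarized by treatment group over time using descriptive statistics". Change and percent change are specified to Week 12. SAP 3.3.6 lists prior and concomitant medications by subject. The SAP describes no analysis that takes account of background changes.

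**The concern.** The trial is open-label with one arm. In the extension there is no concurrent comparison, so stable background treatment is the main safeguard against crediting CCX140-B with the effect of another drug. Protocol Section 1.5 itself describes RAAS blockers as treatment for proteinuria. The exclusion criteria also admit subjects already taking calcineurin inhibitors, other immunotherapy, or glucocorticoids up to 10 mg/day prednisone equivalent.

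The extension is meant to show the degree and duration of response, and the protocol's secondary efficacy objectives run through End of Treatment. If a background dose is raised at discretion and UPCR then falls, the fall appears in the extension data with nothing to separate it from a study-drug effect. Sites also have two instructions for the same weeks, so practice may differ between sites.

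**Working it through.** The documents state no figure to reproduce. The check sets the passages side by side, followed by simple arithmetic on reach.

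**1. Do the rules cover the same weeks?**
- The Methodology and Section 3.1.3 sentence applies throughout the treatment period. In Section 3.1.3 it comes directly after text on dose escalation after 12 weeks, so it cannot be read as limited to the first 12.
- The Section 7.7 permission applies after Week 12 and has no safety condition.
- The two therefore overlap for the whole extension and give different conditions for a change.
- Criterion 6 and the anti-CD20 rule both refer to the whole study, and neither mentions an extension exception.

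**2. Is a permitted change rescue or failure?**
- Take a subject who entered on a RAAS inhibitor or calcineurin inhibitor and whose dose is raised at discretion in the extension.
- Section 7.7 allows it, so the exemption in Section 7.7.1 applies and it need not be rescue.
- Criterion 2 names new immunotherapy. It names neither a dose increase of an existing immunosuppressant nor a RAAS change, so it need not be failure by that route.
- A new immunosuppressant differs: Section 7.7.1 still names it as rescue. Yet Section 7.7 lets such a subject continue if not a treatment failure and if the study director agrees. Those passages also need to be squared with each other.

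**3. What does it reach?**
- Duration: the extension is up to 40 of 52 treatment weeks, 40/52 = 77%.
- Visits: the example eGFR window table in SAP 3.1.2 has 14 post-baseline visits. Ten (Weeks 16 to 52) come after Week 12, 10/14 = 71%.
- Dosing: Section 3.1.2 allows extension escalation only if at least partial remission has not been achieved and maintained. A UPCR fall caused by a background drug could therefore also change study-drug dosing.

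**4. How large a background effect would change remission status?**
Partial remission needs a UPCR reduction of at least 50%, a value below 3.5 g/g, and no treatment failure. If r is the reduction already present at Week 12, the further relative fall needed is 1 − 0.50/(1 − r).

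| r at Week 12 | Further fall needed |
|---|---|
| 20% (one permitted entry route) | 1 − 0.50/0.80 = 37.5% |
| 30% | 1 − 0.50/0.70 = 28.6% |
| 40% | 1 − 0.50/0.60 = 16.7% |

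The documents give no size b for a background-drug effect. With assumed values, and no further study-drug effect from r = 20%, the total reduction is 1 − 0.80 × (1 − b):

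| Assumed b | Total reduction |
|---|---|
| 10% | 28% |
| 20% | 36% |
| 30% | 44% |
| 40% | 52% |

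Only the largest assumed effect crosses 50% from a 20% start. From a 40% start, an effect of 20% would do so. The 3.5 g/g condition must also be met.

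**The case against.** **The contradiction is narrower than a count of passages suggests.** Within Section 7.7 the permission follows the stability rule and can be read as an express extension exception. Criterion 6 is an entry criterion about what is projected. The anti-CD20 rule is specific and can stand as an exception to the general permission. This is fair. The clear clash is with the one sentence in Methodology and Section 3.1.3, but that sentence has no extension exception, so the clash remains.

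**Little in the planned analysis depends on it.** SAP 3.4 says remission, its associated endpoints and time to rescue will not be calculated. SAP 3.1.5 rules out formal testing. Enrollment has stopped and an abbreviated report is planned. With at most 13 subjects, a reader could match listed medications to listed UPCR values by hand. This limits the size of the point, but unflagged listings leave that matching to the reader.

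**Stronger readings that the documents do not support.**
- A reader might infer that the permission could help the trial meet its 20% median reduction. That is a Week 12 criterion, the permission starts after Week 12, and SAP Section 6 replaces the criterion with summary statistics. No 20% median rule applies in the extension.
- A reader might infer that all background treatment is freed. Section 7.7 refers to doses, bars plasmapheresis, and ties continuation after a new immunosuppressant to study director agreement. Starting high-dose glucocorticoids remains named as rescue.
- A reader might infer inflated remission rates in the report. The SAP plans none.

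**Conclusion.** The protocol is wrong as written: it gives two conditions for changing background medication in the same weeks. Section 7.7.1 and Treatment Failure criterion 2 together leave room for a discretionary increase of an existing RAAS inhibitor or immunosuppressant to be neither rescue nor failure.

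The statistical effect is confined to the descriptive extension UPCR and eGFR summaries and listings, and to remission status as a condition for extension escalation. The Week 12 endpoint is untouched.

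This rests on two readings: that the over-time summary in SAP 3.4.1 includes extension visits, although change is specified only to Week 12; and that the Section 7.7.1 exemption covers the extension permission. The size of any bias is unknown, because the documents give neither a background-drug effect nor the expected number of changes. The figures for assumed effects are illustrations only.

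**What to change.** **Protocol.** The sponsor must reconcile the synopsis (Methodology, inclusion criterion 6, Treatment Failure definition) with Sections 3.1.3, 4.2, 5.2.1, 7.7 and 7.7.1. The result should be one background-medication rule, with its relation to rescue and treatment failure stated for before and after Week 12. This review does not say which rule is right.

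**SAP 3.4.1.** Add a supplementary by-visit summary of UPCR and eGFR that leaves out values after the first start or dose increase of a RAAS inhibitor, glucocorticoid or immunosuppressant. Flag those values in the listings. The same summary would also handle RAAS adjustments permitted before Week 12.

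**Cost.** Wording changes, one extra table and one listing flag, using concomitant-medication dates already collected. This assumes that a dose increase is entered as a dated record, which the documents do not spell out. The extra table will hold few values at late visits. Subjects whose background treatment is raised may also differ from the rest, so the table should stand beside the full summary and not replace it.
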